1. TABULAR SUMMARY

Aim	
 • Anaemic patients that otherwise undetected by pre-operative tests recommended by international guidelines • Accuracy of SpHb compared to the gold standard in a pre-operative setting
Endpoints	
 • SpHb measurement pre-operatively • Laboratory Hb measurement pre-operatively • n of detected anaemic patients • n of otherwise (according to pre-operative blood sampling guidelines) undetected anaemic patients
Inclusion criteria	
 • Age > 18 years • Patient is planned for elective surgery • Pre-operative evaluation by an anaesthesiologist • Informed consent
Exclusion criteria	
 • Age <18 years • Patient refusal • Emergency surgery • No central laboratory Hb-test available
Sample size	Approximately 1500 patients
Study site	Div. of General Anaesthesiology, Emergency- and Intensive Care Medicine, Medical University of Graz
Sponsor	
Medical University of Graz
 
Div. of Gen. Anaesthesiology, Emergency- and Intensive Care Medicine, Medical University of Graz, Austria
 
Head: [name], MD, PhD

Investigator	
[name]
 
Div. of Gen. Anaesthesiology, Emergency- and Intensive Care Medicine, Medical University of Graz, Austria

2. SUMMARY

Knowledge of patients' serum haemoglobin (Hb) levels is of great importance in many areas of medical practice. Standard methods of measurement require direct blood sampling; they are therefore relatively invasive, costly, and time-consuming.

Non-invasive Hb measurement techniques utilizing a finger probe (SpHb) have attracted a lot of attention over the last five years. Numerous studies have compared the accuracy of these devices with central laboratory Hb data in a wide range of clinical settings: operating rooms, critical care units, emergency departments, and blood donor clinics. (1-3)

A meta-analysis of previous studies regarding SpHb measurements in perioperative and intensive care settings has revealed a mean difference between non-invasive and central laboratory Hb results of 0.10 ± 1.37 g/dl ($n=4425$) (2) . To date, however, few studies have assessed the use of these devices in a pre-operative setting.

Such a study could be of great value, as Hb measurement plays an important role in the implementation of PBM programmes (Patient Blood Management), which in turn are associated with improved patient outcomes, fewer transfusions and lower costs. (4-7)

Various guidelines with the aim of reducing unnecessary testing have been proposed. Such guidelines prioritize the tests to be applied during preparation for minor, intermediate and major surgery, considering specific comorbidities. (8)

Our goal is to establish SpHb threshold values that can help health care provider sort out which patients would potentially benefit from central laboratory Hb testing pre-operatively and who would likely not. We also aim to compare the mean difference between these two methods in a pre-operative setting.

With reliable cut-off values, SpHb levels could serve as a pre-test for patients with a low ASA score undergoing minor to intermediate surgery—i.e., those who would normally not receive a complete lab-test before an operation. This adaptation of clinical routine could help to detect anaemia where it might otherwise be missed.

To achieve this goal, we will observe and record SpHb values from patients meeting the inclusion criteria undergoing pre-operative evaluation for plastic, trauma, orthopaedic,

urological, general and gynaecological surgery over one year by the Department of Anaesthesiology and Intensive Care Medicine at the University Medical Centre Graz.

All patients will be evaluated pre-operatively by an anaesthesiologist, utilizing both central laboratory measurements as clinical routine and non-invasive Hb measurements. Both measurements (SpHb and central laboratory Hb) will be documented, along with the normally collected patient data, using the electronic system currently in use. Median values from the two methods will be compared, and possible cut-off values calculated.

3. BACKGROUND

3.1. Patient Blood Management (PBM)

According to the World Health Organisation (WHO), patient blood management (PBM) is a "patient-focused, evidence based and systematic approach for optimising the management of patients and transfusion of blood products to ensure high quality and effective patient care". (5)

A growing number of large observational studies and randomised controlled trials suggest that avoiding unnecessary transfusion can reduce morbidity and mortality. (4, 9) The high prevalence of untreated pre-operative anaemia implies a clinically relevant potential to avoid a significant amount of transfusions each year and thereby improve outcomes. (10, 11) In the effort to reduce red blood cell transfusions and detect pre-operative anaemia, preoperative Hb measurement is essential to detect and treat anaemia early.

3.2. Non-invasive haemoglobin measurement

Haemoglobin assessment is one of the most common laboratory tests performed worldwide. The value of a reliable clinical method of measure Hb in patients undergoing major surgery is well established. (4, 10)

The gold standard of Hb measurement involves venepuncture or finger prick. These methods are invasive and costly in terms of both time and resources, not to mention the risk they pose for both patient and clinical staff. These risks include pain, nerve damage, infection and the transmission of diseases.

Non-invasive Hb measurement is performed with a finger probe to measure SpHb without blood sampling. Rad-67™ Spot-check Pulse CO-Oximeter® (Masimo corporation, Irvine,

CA) is a device based on multi-wavelength co-oximetry for the spectrophometric estimation of haemoglobin (SpHb).

The usefulness of continuously measuring SpHb in a perioperative setting has previously been described. Several studies have shown that SpHb can help to estimate Hb values in various settings and to reduce unnecessary red blood cell (RBC) transfusions. It is also useful for Hb trend monitoring during surgery. (2, 12-14)

A meta-analysis by Kim et. al showed that the overall pooled random-effects mean difference (non-invasive vs. central laboratory) and SD were 0.10 ± 1.37 g/dL (-2.59 to 2.80 g/dL, I = 95.9% for mean difference and 95.0% for SD). (2)

In a pre-operative setting SpHb could act as an additional tool to reduce unnecessary testing without the cost of overlooking anaemic patients.

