4. AIM OF THE STUDY

This studies aim is to evaluate the accuracy of non-invasive Hb measurement in a pre-operative setting and its possible role in a PBM approach to detect anaemic patients before surgery.

We will compare SpHb to the gold standard and seek to establish cut-off values that could be used to identify patients that need laboratory Hb measurement irrespective of physical status preoperatively.

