6. STATISTICAL CONSIDERATIONS

6.1. Sample size

The sample size was calculated based on a two-sided confidence interval with a confidence level $1-\alpha$ of 95%, an expected proportion of 0,85 and a distance of proportion to limit of 0,05.

With a prevalence of 14,1%(11) in a pre-operative setting for anemia the sample size needed was calculated to be 1392.

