6.2. Statistical analyses

Mean differences and standard deviation (SD) will be calculated. Accuracy (trueness and precision) of non-invasive Hb measurement will be compared with its gold standard using linear regression analysis and Bland-Altman-analysis.

Potential SpHb cut-offs to reliably non-invasively detect anaemia as defined by the gold-standard will be tested using receiver-operating characteristics (ROC) analysis.

The theoretical number of patients with anaemia that would remain undetected by strict application of existing guidelines concerning preoperative laboratory measurements will be expressed as a total amount within the patient cohort and as an incidence per 100.000 patients.

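### The guideline-missed anaemia count uses no SpHb result and the ROC analysis pools all patients, so the plan does not show which missed cases SpHb would recover or which guideline-tested cases it could screen out

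*Combined protocol and SAP*

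**What the plan says.** Two endpoints in the tabular summary (section 1) are counts of patients: the number "of detected anaemic patients", with no method or testing strategy named, and the number "of otherwise (according to pre-operative blood sampling guidelines) undetected anaemic patients". Section 6.2 develops the second: "The theoretical number of patients with anaemia that would remain undetected by strict application of existing guidelines concerning preoperative laboratory measurements" is to be given as a total and per 100,000 patients.

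The only planned analysis of SpHb as a classifier is in section 6.2: "Potential SpHb cut-offs to reliably non-invasively detect anaemia as defined by the gold-standard will be tested using receiver-operating characteristics (ROC) analysis". It is not split by whether the guidelines would call for a laboratory test.

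On intended use, the text points two ways.

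- **Add-on use.** Research question 1 (4.1) and hypothesis 2b (4.2) ask whether SpHb finds anaemia in patients who would otherwise go untested. Section 2 names patients with a low ASA score having minor to intermediate surgery.
- **Triage use.** The goal in section 2 is thresholds to "sort out which patients would potentially benefit from central laboratory Hb testing pre-operatively and who would likely not". The aim in section 4 is cut-offs to "identify patients that need laboratory Hb measurement irrespective of physical status preoperatively". The background in 3.2 adds the prospect of less testing: "In a pre-operative setting SpHb could act as an additional tool to reduce unnecessary testing without the cost of overlooking anaemic patients".

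**The concern.** The guideline-missed count is fixed by laboratory Hb and the guideline rules. A perfect device and a useless one would give the same number. It measures the gap that SpHb might fill, not how much of it SpHb fills, which is what research question 1 and hypothesis 2b ask.

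The pooled ROC analysis does not supply the missing part. Its sensitivity mixes anaemic patients the guidelines would test with those they would not. For add-on use, the sensitivity that matters is the one in the second group. For triage use, the loss that matters is in the first group: anaemic patients who would have been tested but whose SpHb lies above the cut-off. Neither is a planned output, and neither is the number of laboratory tests saved or added.

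At stake is whether the trial can answer its first research question, and whether a conclusion about less testing without overlooked anaemia would rest on a reported figure.

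**Working it through.** **1. Reproduce the plan's sample size.** Section 6.1 gives a two-sided 95% confidence level, "an expected proportion of 0,85 and a distance of proportion to limit of 0,05", and a prevalence of 14.1%.

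- Anaemic patients: 1.96² × 0.85 × 0.15 / 0.05² = 195.9, rounded up to 196.
- All patients: 196 / 0.141 = 1390.1, rounded up to 1391. The plan states 1392.
- Treating 0.85 as a specificity gives 196 / 0.859 = 228.2, so about 229, which does not match. The 0.85 is therefore acting as a sensitivity, although 6.1 does not name it.

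**2. Overall SpHb misses.** With D = 196 anaemic patients and sensitivity Se = 0.85, the number above the cut-off is (1 − 0.85) × 196 = 29.4. Per 100,000 patients this is 0.141 × 0.15 × 100,000 = 2,115. The planned ROC analysis would yield this figure at any chosen cut-off.

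**3. What the planned outputs determine.** Let f be the share of anaemic patients the guidelines would test. The documents do not give f, so a range is assumed. If SpHb alone decides who is tested:

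- Missed by the guidelines: (1 − f)D. This is the planned count.
- Missed by SpHb: (1 − Se)D, from the pooled ROC analysis.
- Net change in detection: (1 − f)D − (1 − Se)D = (Se − f)D. Both terms are obtainable, so the net is too.

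**4. What they do not determine.** Net equals recovered minus lost. If sensitivity is the same in both groups, recovered = Se(1 − f)D and lost = (1 − Se)fD. If it may differ, the 29.4 misses can fall in either group, and the last two columns show the possible range.

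| f (assumed) | Guideline-missed | Net | Recovered, equal Se | Lost, equal Se | Recovered, range | Lost, range |
|---|---|---|---|---|---|---|
| 0.50 | 98.0 | +68.6 | 83.3 | 14.7 | 68.6 to 98.0 | 0 to 29.4 |
| 0.70 | 58.8 | +29.4 | 50.0 | 20.6 | 29.4 to 58.8 | 0 to 29.4 |
| 0.85 | 29.4 | 0 | 25.0 | 25.0 | 0 to 29.4 | 0 to 29.4 |
| 0.90 | 19.6 | −9.8 | 16.7 | 26.5 | 0 to 19.6 | 9.8 to 29.4 |
| 0.95 | 9.8 | −19.6 | 8.3 | 27.9 | 0 to 9.8 | 19.6 to 29.4 |

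At f = 0.85, for example, the planned outputs fit SpHb recovering every guideline-missed case and equally fit it recovering none. Break-even is at f = Se. At Se = 0.80, the lower limit of the planned interval, it moves to f = 0.80, and f = 0.90 gives (0.80 − 0.90) × 196 = −19.6.

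Under add-on use the lost column is zero for every f, but the recovered column is still undetermined.

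**5. Tests ordered.** The number below the SpHb cut-off follows from pooled sensitivity, specificity and prevalence. The number under a guideline-or-SpHb rule is guideline tests plus SpHb-flagged patients minus those in both. No planned output gives that overlap.

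**6. Precision by group.** At Se = 0.85 and f = 0.50 each group has 98 anaemic patients, and the half-width is 1.96 × √(0.1275 / 98) = 0.071. At f = 0.85 the guideline-missed group has 29.4, and the half-width is 1.96 × √(0.1275 / 29.4) = 0.129. The planned half-width of 0.05 applies only to the pooled estimate.

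**The case against.** The strongest reply is that the plan already lets a reader compare the two strategies. The whole-cohort ROC analysis gives total SpHb misses, the guideline count gives total guideline misses, and every analysed patient has a laboratory Hb because section 5.1 excludes those without one. This stands. A reader might infer that only the guidelines' misses are counted, so that the plan could report success while detection gets worse. The documents do not support that: with f = 0.90 and Se = 0.85, 19.6 guideline misses against 29.4 SpHb misses would show the loss.

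Second, the sentence on reducing testing is background, worded as a possibility. It is not among the stated aims, research questions or hypotheses. This also stands.

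Third, the triage reading can be contested. The aim in section 4 may mean flagging patients whose good physical status would not trigger a test, rather than cancelling tests the guidelines call for. Sections 2 and 7.1 describe laboratory Hb as routine in this clinic, so the testing to be reduced may be local practice rather than guideline-indicated tests. On that reading no guideline-tested case is lost. The reading is plausible, but the documents never choose it, and the goal in section 2 also speaks of patients who would likely not benefit from a test.

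Fourth, the number of detected anaemic patients could be defined so as to show the split. It could, but as written it is not.

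None of this supplies the breakdown by guideline status. The add-on reading needs it as well, because recovered cases are the answer to research question 1.

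**Conclusion.** The point holds in a limited form. The planned outputs give total misses under each approach and hence the net difference. They do not give the guideline-missed anaemic patients that SpHb recovers, the guideline-tested ones it would screen out under triage, or the tests ordered under a combined rule.

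The size rests on D = 196 (14.1% prevalence, 1392 patients), on 0.85 being a sensitivity, and on an assumed f. A fall in net detection requires an SpHb-only rule and guidelines that already test more than about 85% of anaemic patients. A reader might infer that such a fall is likely; the documents give no value of f from which to say so. Even where net detection improves, an SpHb-only rule would leave the claim of no overlooked anaemia unsupported for any guideline-tested patients it screened out.

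This is a cheap improvement that lets the trial answer its own first question. It is not a flaw that invalidates the design.

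**What to change.** In section 6.2:

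1. State whether SpHb is meant to add to guideline-indicated testing or to replace it.
2. Classify every patient by guideline test (yes/no), SpHb (below/above the chosen cut-off) and laboratory anaemia (yes/no).
3. Report, with confidence intervals (paired for the net difference), the anaemic patients recovered, lost and net, and the laboratory tests ordered, under three theoretical strategies: guideline only, SpHb only, and guideline or SpHb.
4. Limit any conclusion on reduced testing without overlooked anaemia to what this table shows.

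In section 1, define the number of detected anaemic patients by method and strategy so that it matches the table.

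The cost is one more table, with no new patients or procedures. Guideline status must already be assigned to the anaemic patients for the planned count; the tests-ordered figures need it for everyone. Estimates within each guideline group will be less precise than ±5 points and should be labelled as such.

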4. AIM OF THE STUDY

This studies aim is to evaluate the accuracy of non-invasive Hb measurement in a pre-operative setting and its possible role in a PBM approach to detect anaemic patients before surgery.

We will compare SpHb to the gold standard and seek to establish cut-off values that could be used to identify patients that need laboratory Hb measurement irrespective of physical status preoperatively.

4.1. Research questions

Research question 1: Can we use non-invasive Hb measurement as a pre-test to detect patients that are anaemic but would normally not get a central laboratory test?

Research question 2: Can we establish cut-off values for SpHb in a pre-operative setting?

Research question 3: How accurate is SpHb in a pre-operative setting for patients undergoing different kinds of surgery compared to the gold standard?

4.2. Hypotheses

Null Hypothesis h01a: SpHb measurement adds no benefit to the pre-operative evaluation of patients undergoing surgery.

Alternative Hypothesis ha1a: SpHb measurement is an easy and safe way to detect anaemic patients in a pre-operative setting who would normally be missed by clinical routine.

Null Hypothesis h02b: SpHb measurement cannot detect anaemic patients that would normally be missed by pre-operative evaluation recommended by current guidelines.

Alternative Hypothesis ha2b: SpHb measurement can detect anaemic patients that would normally be missed by pre-operative evaluation recommended by current guidelines.

Null Hypothesis h03a: The accuracy of non-invasive Hb measurement in a pre-operative setting is inferior to its already proven accuracy in other settings.

Alternative Hypothesis ha3a: The accuracy of non-invasive Hb measurement in a pre-operative setting is non-inferior to its already proven accuracy in other settings.

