5. METHODS

This study is planned to be carried out as a prospective application study in a pre-operative clinic. Adult patients planned to undergo pre-operative examination and evaluation by an anaesthesiologist for elective surgery are to be included (see paragraph 5.1. for full inclusion and exclusion criteria).

Included patients will be evaluated by an anaesthesiologist according to national and international guidelines as it is routine at the pre-operative clinic. In addition, all included patients will have their Hb measured non-invasively by a trained health care provider. SpHb values will be recorded in the documentation software already in use at the clinic.

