7. ETHICAL CONSIDERATIONS

7.1. Potential risks and benefits

SpHb measurement, the only protocol-based procedure to be performed in patients included into this study, is a non-invasive application with no known potential to harm included patients. Venepuncture and laboratory measurement of haemoglobin concentration are part of the current routine practice in the preoperative clinic in question; patients are therefore not expected to directly benefit from the participation in this study.

Findings from this study, however, might lead to a better understanding of how non-invasive Hb measurement could be used in the future. Current supranational guidelines do not recommend Hb measurement for every patient undergoing specific surgery. With this clinical practice, health care providers might miss some anaemic patients, who might then be treated inappropriately.

The prevalence of pre-operative anaemia varies largely between different patient groups depending on age, comorbidities, planned surgery, etc. Lasocki et al. found that 14,1% of patients ($n=1534$) planned to undergo major elective hip, knee or spine surgery were anaemic. After surgery, the number of anaemic patients increased up to 85,8%. In PBM vs. non-PBM centres, preoperative anaemia was less frequent (8,0% vs. 18,5%). (11)

As undetected anaemia represents a major problem in clinical routine, (6, 10, 15, 16) SpHb measurement could work as a pre-test in this scenario, to help health care providers in their decision-making process.

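### Hypothesis 1 claims benefit, ease and safety that nothing measures, and no planned result says how many guideline-missed anaemic patients SpHb would detect

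*Combined protocol and SAP*

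**What the plan says.** Section 4.2 sets the first null, "SpHb measurement adds no benefit to the pre-operative evaluation of patients undergoing surgery", against the alternative that "SpHb measurement is an easy and safe way to detect anaemic patients in a pre-operative setting who would normally be missed by clinical routine". The second alternative in the same section is narrower: "SpHb measurement can detect anaemic patients that would normally be missed by pre-operative evaluation recommended by current guidelines".

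The endpoints in section 1 are two haemoglobin values (the first is "SpHb measurement pre-operatively", the second its laboratory counterpart) and two counts: anaemic patients detected, and the number "of otherwise (according to pre-operative blood sampling guidelines) undetected anaemic patients".

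Section 6.2 plans mean differences with SD, linear regression, Bland-Altman analysis and ROC analysis against laboratory Hb. It adds one descriptive figure, "The theoretical number of patients with anaemia that would remain undetected by strict application of existing guidelines concerning preoperative laboratory measurements", given as a total and per 100,000 patients. It assigns no test, threshold or estimate to hypothesis 1.

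There is one group. Section 5 says that "all included patients will have their Hb measured non-invasively by a trained health care provider", and section 5.1 excludes patients who have no laboratory Hb.

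Routine is described in two ways. Section 7.1 says "Venepuncture and laboratory measurement of haemoglobin concentration are part of the current routine practice in the preoperative clinic in question", and the end of section 2 likewise treats the laboratory measurement as routine for all patients. Section 5 instead describes the clinic's routine as evaluation according to guidelines, and section 7.1 itself notes that guidelines do not call for Hb in every surgical patient.

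**The concern.** A hypothesis should point to something the study measures. Three of the ideas in hypothesis 1 (benefit, ease, safety) point to nothing in the endpoint list. The fourth, detection of patients missed by routine, depends on a term the protocol uses in two senses. Under one of them, no analysed patient can be missed.

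Detection matters most, because research question 1 asks whether SpHb can serve as a pre-test in patients who would not ordinarily have a laboratory test. If the report contains an overall ROC curve and a count of guideline-missed anaemia, a reader may put the two together and take the count as the yield of SpHb. It is not. There is a related gap for failed readings: a patient with no SpHb value cannot enter the ROC or Bland-Altman analysis, although failures bear on both ease of use and the value of a pre-test.

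**Working it through.** **1. Each claim against what is measured**

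| Claim in hypothesis 1 | Endpoint (section 1) | Analysis (section 6.2) |
|---|---|---|
| Benefit | none | none |
| Easy | none | none |
| Safe | none; section 7.1 asserts absence of known harm | none |
| Detects missed anaemia | count of guideline-missed patients | count and incidence; ROC in all patients |

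The null (no benefit) and the alternative (easy, safe, detects) are also not complements. Rejecting the first would not establish the second.

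**2. What the guideline-missed count contains**

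Let M be the number of patients who are anaemic by laboratory Hb and for whom the guideline indicates no test. Let S be the number of these whom SpHb flags at the chosen cut-off. Section 6.2 reports M. M depends on laboratory Hb and the guideline rule only, so it would be the same had SpHb never been measured. Research question 1 and hypothesis 2 need S/M, which is not planned.

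**3. Whether the overall ROC fills the gap**

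Write the sensitivity in all anaemic patients as w × Se(missed) + (1 − w) × Se(tested), where w is the guideline-missed share of anaemic patients. Section 6.1 gives an expected proportion of 0.85 without labelling it; take it as overall sensitivity. The lowest Se(missed) compatible with 0.85 occurs when Se(tested) = 1, and equals (0.85 − (1 − w)) / w. The share w is not in the documents; 10%, 25% and 50% are assumed.

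- w = 0.50: (0.85 − 0.50) / 0.50 = 0.70
- w = 0.25: (0.85 − 0.75) / 0.25 = 0.40
- w = 0.10: (0.85 − 0.90) / 0.10 is negative, so the bound is 0

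The upper bound is 1 in each case. These are logical limits, not predictions, but they show that the pooled figure does not determine the one that is wanted.

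**4. Precision in the subgroup**

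The plan's own figure first (section 6.1: 95% confidence, 0.85, distance 0.05, prevalence 14.1%): 1.96² × 0.85 × 0.15 / 0.05² = 195.9, so 196 anaemic patients. Then 196 / 0.141 = 1390.1, so 1391 against the stated 1392, which agrees.

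Half-width = 1.96 × √(0.85 × 0.15 / m), with m = 1392 × 0.141 × w:

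| Assumed w | m | 95% half-width |
|---|---|---|
| 10% | 20 | 0.16 |
| 25% | 49 | 0.10 |
| 50% | 98 | 0.07 |

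With w = 25% and the other prevalences quoted in section 7.1, m is 28 at 8.0% (half-width 0.13) and 64 at 18.5% (half-width 0.09).

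**5. Failed readings**

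No failure rate f is given; 2% to 10% is assumed. If 0.85 is sensitivity, failures are unrelated to anaemia, and a failure counts as not detected, detection among all patients offered the test is 0.85 × (1 − f):

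- f = 2%: 0.833
- f = 5%: 0.808 (0.8075 before rounding)
- f = 10%: 0.765

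**The case against.** The best defence is that a one-group study with paired measurements is the normal way to study detection, that universal laboratory Hb is what supplies the reference standard, and that hypothesis 2 already carries the guideline wording. All of this stands. A reader might infer that the design cannot address detection at all; the documents do not support that. The data needed for S/M would be collected once the guideline rule is applied to each patient. What is missing is the planned tabulation.

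A reader might also infer that the comparator is simply empty because this clinic tests everyone. Sections 2 and 7.1 lean that way, and every analysed patient does have a laboratory Hb. But section 5 describes routine as guideline-based, the hypothesis is worded counterfactually, section 6.2 calls its count theoretical, and the exclusion for lack of a laboratory test implies that some clinic patients may not have one. The fair criticism is inconsistent use of the term.

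On failed readings, section 5.3 keeps one line per patient, so a missing SpHb would appear as a blank. That is true, but section 5.2 names no field that would separate a failed reading from one not attempted. Counting failures as missed cases is a worst case, because the protocol does not say what follows a failed reading.

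Finally, it is speculative to say that the study will declare SpHb beneficial, easy and safe. Section 4 speaks only of a possible role. The point is that the hypothesis as worded invites a conclusion the data could not support.

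**Conclusion.** The point holds in this form. Hypothesis 1 cannot be tested as written: benefit, ease and safety have no endpoint or analysis, its null and alternative are not complements, and its comparator is used in two senses. The detection question can be answered from the planned measurements, but no planned result answers it.

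The size depends on figures that the documents do not give. Subgroup half-widths of about 0.07 to 0.16 rest on assumed guideline-missed shares of 50% down to 10%, the planned prevalence and a proportion of 0.85. The failed-reading figures of 0.833 to 0.765 are illustrative and rest on the three assumptions stated with them. It is tempting to divide 0.05 by 0.85 and say that a failure rate of 5.9% would exhaust the planned margin. That would be wrong: the 0.05 in section 6.1 is the distance from the estimate to its confidence limit, not a tolerated loss of sensitivity.

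The overall accuracy analyses and the sample size figure are unaffected.

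**What to change.** - Remove benefit, ease and safety as conclusions of hypothesis 1.
- Replace clinical routine with a named guideline rule, applied to each patient and recorded as test indicated or not indicated. Since this brings hypothesis 1 close to hypothesis 2, merge the two.
- Prespecify in section 6.2 the proportion of guideline-missed anaemic patients whom SpHb flags at the chosen cut-off, with a 95% confidence interval. Report alongside it the number flagged among non-anaemic patients for whom the guideline indicates no test, so that false alarms are visible.
- Add a field for whether an SpHb reading was obtained. Report the failure rate, and give detection among patients with a reading and, as a worst-case sensitivity analysis, with failures counted as not detected.

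The cost is protocol wording, one data field for readings and one extra tabulation; the guideline classification is already implied by the planned count. The downside is a narrower claim and a less precise estimate, because it rests on a subgroup of the anaemic patients.

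### h02b/ha2b have no chance benchmark, and section 6.2 plans no analysis of SpHb within the patients the guideline would leave untested

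*Combined protocol and SAP*

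**What the plan says.** Section 4.2 gives the null as "Null Hypothesis h02b: SpHb measurement cannot detect anaemic patients that would normally be missed by pre-operative evaluation recommended by current guidelines" and the alternative as "Alternative Hypothesis ha2b: SpHb measurement can detect anaemic patients that would normally be missed by pre-operative evaluation recommended by current guidelines". Neither statement has a threshold, a comparator or a limit on false positives.

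The endpoint row of the tabular summary (section 1) lists SpHb, laboratory Hb and two counts. One is the number "of detected anaemic patients", without saying by which method they are detected. The other is the number of anaemic patients who would go undetected under the blood-sampling guidelines.

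Section 6.2 plans three analyses that bear on this point:

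- Regression and Bland-Altman analysis of SpHb against the laboratory value.
- ROC analysis to find SpHb cut-offs for anaemia, with no subgroup named and no success criterion.
- A count, and a rate per 100,000, of anaemic patients whom strict use of the guidelines would miss.

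The only numerical performance target is in section 6.1: "an expected proportion of 0,85 and a distance of proportion to limit of 0,05". The plan does not name that proportion or link it to h02b.

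**The concern.** Research question 1 (section 4.1) asks whether SpHb can serve as a pre-test in patients who would not normally get a laboratory test. The summary (section 2) names the intended users: patients with a low ASA score having minor to intermediate surgery. h02b/ha2b is the hypothesis pair that addresses this most directly.

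Two things are missing. First, the null is set against no detection at all, not against what flagging by chance would give. Any cut-off that flags a fair share of patients is likely to flag some guideline-missed anaemic patients, whether or not SpHb carries information about them. Secondly, none of the analyses in section 6.2 looks at SpHb inside the guideline-exempt group. The ROC covers anaemia in general, and the count of missed patients describes the guideline, not the device.

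At stake is a positive statement on research question 1 that rests on a bare count, or on accuracy in a cohort that includes patients who would have been tested anyway.

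**Working it through.** **The plan's own figure.** Inputs from section 6.1: 95% two-sided interval, proportion 0.85, half-width 0.05, prevalence 14.1%.

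- Anaemic patients needed: 1.96² × 0.85 × 0.15 / 0.05² = 195.9, rounded up to 196.
- Total: 196 / 0.141 = 1390.07, rounded up to 1391.

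This agrees with the stated 1392 to within rounding, so the sample size is not at fault. It is sized on all anaemic patients in the cohort, about 1392 × 0.141 = 196, and not on those the guideline misses.

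**Chance detections under the literal null.** Let f be the share of patients flagged by a device unrelated to Hb, and m the number of guideline-missed anaemic patients. Then

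P(at least one detection) = 1 − (1 − f)^m.

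The documents give neither f nor m. The range assumed for m takes 20% to 50% of patients as guideline-exempt and 3% to 8% of those as anaemic:

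- low: 1392 × 0.20 × 0.03 = 8.4, about 8;
- high: 1392 × 0.50 × 0.08 = 55.7, about 56.

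| f | m | P(at least one) |
|---|---|---|
| 1% | 8 | 0.08 |
| 5% | 8 | 0.34 |
| 10% | 8 | 0.57 |
| 14.1% | 20 | 0.952 |
| 30% | 56 | >0.999 |

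**Would a chance-benchmarked null be workable?** A one-sided 2.5% Mann-Whitney test of SpHb in anaemic versus non-anaemic exempt patients tests whether the AUC exceeds 0.5. It was simulated with bias 0.10 and error SD 1.37 g/dL, the pooled values from the meta-analysis in section 3.2, and an assumed Hb SD of 1.4 g/dL.

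| Exempt patients | Anaemic | Power | Mean AUC |
|---|---|---|---|
| 278 | 3% | 0.99 | 0.92 |
| 417 | 5% | 1.00 | 0.90 |
| 696 | 8% | 1.00 | 0.89 |

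An uninformative device was accepted in 2.1% to 2.7% of simulated studies, which is close to nominal.

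**Is AUC above 0.5 enough?** No. With 696 exempt patients, 8% anaemic, and an error SD of 5 g/dL (assumed, far worse than the published value), the AUC is about 0.65 and the test still succeeds about 97% of the time. Beating chance does not show usefulness as a pre-test.

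**Precision in the target group.** The half-width at a sensitivity of 0.85 is 1.96 × √(0.85 × 0.15 / m):

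- m = 196: 0.05
- m = 56: 0.09
- m = 49: 0.10
- m = 20: 0.16
- m = 8: 0.25 (only indicative, as the normal approximation fails at this size)

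**The case against.** The strongest reply is that the plan never says one detection rejects h02b. The wording is ordinary clinical language, and the zero-detection null is its most literal reading. The plan also includes analyses that would expose a useless device. The ROC sets sensitivity against false positives and would show an AUC near 0.5, and the regression and Bland-Altman results would point the same way. SpHb and laboratory Hb are both recorded, so false positives can be calculated from planned data.

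Much of this stands. A reader might infer that ha2b cannot fail, or that any device would confirm it. The documents do not support that. No such decision rule is written. The chance probability depends on an f and an m that the plan does not give, and it is low when few patients are flagged. The whole-cohort ROC would reveal a device with no information. Nor can the endpoint count of detected anaemic patients be read as a count of SpHb true positives, since it does not name the method.

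What the reply does not remove is that the ROC is neither linked to h02b nor confined to guideline-exempt patients, and has no success criterion. A satisfactory AUC in the whole cohort does not establish discrimination among patients the guideline leaves untested, whose case mix may differ.

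**Conclusion.** The point holds as a gap in specification. h02b/ha2b lack a chance benchmark, and section 6.2 does not analyse SpHb in the group that research question 1 concerns. Under the literal wording, chance alone would probably yield a supporting detection if 10% or more of patients are flagged: 0.57 to more than 0.999 for 8 to 56 missed cases. Those figures rest on assumed values of f and m.

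The power figures rest on an assumed Hb SD and on the published error SD carrying over to this setting. They indicate that a device performing as published would very probably meet a chance-benchmarked criterion, even with about 8 missed cases. The gap should be closed before the analysis; it does not call the sample-size arithmetic or the data collection into question.

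**What to change.** **Section 4.2.** Restate h02b as: among patients for whom the guideline orders no Hb test, SpHb does not discriminate anaemic from non-anaemic patients (AUC ≤ 0.5). Restate ha2b as AUC > 0.5, shown by the lower 95% confidence limit. Say that this is a minimum requirement only. Do not gloss AUC ≤ 0.5 as sensitivity no higher than the false-positive rate: AUC averages over cut-offs, so the two are not equivalent at a chosen cut-off.

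**Section 6.2.** Run the ROC analysis in that group. At the chosen SpHb cut-off, report sensitivity and specificity with 95% confidence intervals, and give the number of non-anaemic patients flagged beside the number of guideline-missed anaemic patients detected. Base any conclusion about use as a pre-test on these estimates, not on a bare count or on AUC > 0.5. Bring the endpoint row in section 1 into line and name the method of detection.

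**Cost.** Some rewording and one further ROC analysis, with no added patients or measurements, because every included patient has both Hb values. Guideline status must be assigned to non-anaemic patients too, whereas the count already planned needs it only for anaemic ones. The group holds fewer anaemic patients than the cohort, so its sensitivity interval will be wider than ±0.05. The restated ha2b is also open to failure on a defined criterion.
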